4.1 Inclusion Criteria

- Ages 60-89 yrs
- BMI between 18 and 45 kg/m²
- Any ethnicity
- Presence of mild-to-moderate heart failure (NYHA II or III symptomatology) as evidenced by prescribed diuretics or reported shortness of breath upon exertion.

4.2 Exclusion Criteria

- Allergic to milk or soy products
- Hemoglobin <10 g/dL
- eGFR < 30
- Inability to perform strength and/or functional assessments
- Myocardial infarction in the past 6 months
- Unstable angina
- Moderate-severe heart valve disease
- Infiltrative, restrictive or hypertrophic cardiomyopathy
- Dementia –determined by a SLUMS score of <20

- Currently has inflammatory bowel disease
- Received chemotherapy or radiation therapy within the past 12 months
- Currently undergoing tube feeding
- Currently receiving palliative care for end-of-life circumstance
- Unwilling to refrain from using non-study protein/amino acid supplements during their participation in this study
- If deemed medically unstable by the study physician for any other reason.

5.0 Risks and Benefits

There are no direct benefits for the subjects apart from the possibility getting knowledge of their own results of the assessments and blood tests. Expected risks associated with this protocol are described in detail below. All experimental procedures will be performed by appropriately trained and credentialed personnel.

5.1 Blood, urine and fecal sampling:

The total amount of blood taken will be approximately 100 mL. Subjects will have no noticeable effects. The risks of collecting blood samples include pain, bruising and bleeding.

Urine samples will be tested using commercial dipsticks for proteinuria during visits 2 and 14.

Urine collected between visits 1-2 and 13-14 will be analyzed in the PI's lab for the isotope-labelled creatinine to determine skeletal muscle mass (14). There is no risk of collecting voided urine. Fecal samples will be collected at visits 2 and 14. There are no risks associated with collecting fecal samples.

5.2 DEXA scan:

The DEXA scan exposes subjects to approximately ½ of the radiation of one chest x-ray. They will undergo 2 DEXA scans in total.

5.3 Exercise testing (strength and functional):

Subjects may become sore or fatigued during or after the exercise tests. Study staff will remain close to subjects for safety, in the case of dizziness or potential falls. Tests will be paused or stopped if the participant is tired or short of breath. Tests will also be stopped if, for any reason, there is concern about the subject's safety. During the 6-minute walk test, subjects will wear a portable oxygen saturation monitor to allow study staff to observe for desaturation.

5.4 Study supplements:

There are potential allergens in the placebo: milk and soy. All components of EAA mixture (Table 4) are classified as Generally Regarded as Safe (GRAS) by the FDA. They will be provided by PrinovaUSA, which has all necessary certifications for safe production of dietary supplements.

5.5 Confidentiality:

A potential risk to study participants is the potential for loss of confidentiality. Measures to protect the confidentiality of study participants will be implemented as described in the Data Handling and Recordkeeping section below.

5.6 Oral isotope ingestion:

There are no known risks to ingesting 30mg of stable isotope-labelled creatine.

6.0 Data Handling and Recordkeeping

Source documents and CRFs will be stored in a secure area of the PI's laboratory. Access will be limited to study personnel. Documents containing identifiers (except the signed ICF) will be destroyed by shredding approximately 7 years after data analysis is completed or publication of data; whichever is longest. The original, signed ICF will be kept indefinitely. At no time shall Protected Health Information be released to non-study personnel.

The Principal Investigator will carefully monitor study procedures to protect the safety of research subjects, the quality of the data and the integrity of the study. All study subject

material will be assigned a unique identifying code or number. The key to the code (the instrument associating the data with subject identity) will be kept on a password-protected UAMS server, located behind locked doors in a restricted access area of the UAMS campus. Only those individuals listed on the title page of this protocol and their research staff members will have access to the code and information that identifies the subject in this study. This file will be deleted approximately 7 years after data analysis is completed.

7.0 Data Analysis

7.1 Statistical Analysis plan

A repeated measures analysis of covariance (ANCOVA) model will be used to evaluate the effects of EAA mixture and placebo on each parameter. The model will contain EAA mixture versus placebo and time main effects as well as their interaction. Baseline measures will be included in the model as a covariate to control for each subject's starting point. The model will also include factors to account for lean body mass and gender. A non-significant interaction would imply that the EAA mixture or placebo and time effects are not dependent upon one another and that main effects can be tested. The significance of the interaction and main effects will be determined using a 5% α -level. Covariates that may need to be accounted for such as age and lean body mass may be added to the model as a separate exploratory analysis.

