7.2 Significant Interaction Analysis Plan

A significant interaction suggests that the EAA mixture or placebo effect is dependent upon the time effect. This implies the EAA mixture or placebo effect will have to be assessed separately within each time point, and vice versa. Since the two EAA mixture and placebo groups are independent, an analysis of covariance (ANCOVA) model will be used to assess the EAA mixture or placebo effect for each time point (midpoint & final). A repeated measures analysis of variance (ANOVA) model will be used to assess the time effect for EAA mixture or placebo, where the repeated measure is time. A Bonferroni-corrected α -level of 2.5% will be used to determine the statistical significance of these tests.

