7.3 Sample Size Calculation & Power Analysis

A total of 60 completed subjects will be required for this study with 30 subjects per EAA mixture and placebo group. The following power calculations are based on the analysis of the results of the six minute walk, leg strength, grip strength and 10 meter gait speed from our pilot studies. Insulin sensitivity and plasma lipids will be secondary end points. These calculations assume the “worst case” scenario where a significant EAA mixture or placebo-by-time interaction is detected and the covariates are not significant. In this case, the EAA mixture or placebo effect would be assessed separately within each time point, and the time effect would be assessed for each group.

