7.4 EAA mixture or placebo Effect

The following power calculations are based on a two-sample t-test which is being used as an approximation of the ANCOVA model. With 30 subjects in each EAA mixture and placebo group and an α -level of 2.5%, a two-sample t-test will have approximately 80% power to detect effect sizes of 0.82 standard deviation units or larger. **Table 4** presents the hypothesized group means for each endpoint as well as the corresponding EAA mixture or placebo effect and power estimate. These estimates correspond to approximately 25% (6-minute walk) to 50% (gait speed) of the differences in the values between individuals with heart failure vs age-matched healthy controls as determined in our Phase I protocol. Our previous outcome studies with EAAs indicate that these levels of improvement are expected (e.g., 11, 12, 13).

Table 4. Hypothesized group means and within group standard deviation used to estimate the power of the nutritional therapy effect when N=60 (30 per group) are enrolled. The calculations assume that an α -level of 2.5% will be used to determine statistical significance.

Endpoint	Hypothesized Mean Changes [#]		σ_{Δ} ^{\$}	Effect Size	Power (%)
	Control	Nutritional product			
6 Minute Walk ^a	0	105.1	89.3	1.18	98.67
Leg Strength ^a	0	11.0	13.3	0.83	81.31
Grip Strength ^a	0	4.1	4.6	0.89	87.19
10m Gait Speed ^a	0	0.23	0.28	0.82	80.80

#Means of the baseline and post-treatment changes for each group.

§Estimated within group standard deviation of the changes.

^aEstimates of σ_{Δ} were obtained from pilot studies performed at the UAMS Pepper Center.

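### No primary endpoint is named and nothing controls error across the three scheduled function endpoints: about 11-18% false positives if any one success counts (about 5-9% favouring EAA).

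*Combined protocol and SAP*

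**What the plan says.** Section 7.1 applies one model to every parameter: "A repeated measures analysis of covariance (ANCOVA) model will be used to evaluate the effects of EAA mixture and placebo on each parameter". It adds that "The significance of the interaction and main effects will be determined using a 5"% level, and that "A non-significant interaction would imply that the EAA mixture or placebo and time effects are not dependent upon one another", after which the main effects are tested.

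If the interaction is significant, Section 7.2 fits an ANCOVA to "assess the EAA mixture or placebo effect for each time point (midpoint & final"), with repeated-measures ANOVA for the time effect in each group. There a Bonferroni-corrected "level of 2.5% will be used to determine the statistical significance of these tests". That level is 5%/2.

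Section 7.3 bases power on the "six minute walk, leg strength, grip strength and 10 meter gait speed from our pilot studies", and then says "Insulin sensitivity and plasma lipids will be secondary end points". The four powered endpoints therefore read as the main ones, but none is called primary and no rule says how many must succeed. The Table of Events and Section 3.1 schedule 6-minute walk, leg strength (each leg) and grip strength (both hands) at Visits 2, 8 and 14. They do not schedule 10 m gait speed.

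On timing, Hypothesis 1 (Section 2.0) speaks of 12 weeks of intake, and a footnote to Table 4 describes the powered quantity as the change from baseline to post-treatment. Section 1.0 compares weeks 6 and 12 with week -1 without ranking them.

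**The concern.** Hypothesis 1 is about a domain, physical function, and not about a named test. With three scheduled function endpoints, each tested at its own 5%, a significant result on any one could be presented as confirming the hypothesis. The 2.5% level does not prevent this, because it divides by two tests within an endpoint and not by the number of endpoints.

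At stake is what a positive result would mean. Without a named test and a rule across endpoints, the error rate of the claim that the product improves physical function is undefined. If one success suffices, it is well above the level stated for each test.

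**Working it through.** **Inputs.** 30 completers per group (Section 7.3); 5% for interaction and main effects (Section 7.1); 2.5% per time point after a significant interaction (Section 7.2); two-sample t-test as the approximation to ANCOVA (Section 7.4); correlation between midpoint and final of 0.25, 0.50 and 0.75 (Table 5). The correlation between endpoints is not in the documents, so 0 to 0.8 is assumed.

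**Step 1: reproduce Table 4.** Power of a t-test with 58 df, noncentrality d × √(30/2), where d = mean change / SD, at two-sided 2.5%:

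| Endpoint | d | Table 4 power | Recomputed |
|---|---|---|---|
| 6-minute walk | 105.1/89.3 = 1.18 | 98.67% | 98.67% |
| Leg strength | 11.0/13.3 = 0.83 | 81.31% | 81.38% |
| Grip strength | 4.1/4.6 = 0.89 | 87.19% | 87.19% |
| 10 m gait speed | 0.23/0.28 = 0.82 | 80.80% | 80.80% |

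This agrees with the statement in Section 7.4 that the test "will have approximately 80% power to detect effect sizes of 0.82 standard deviation units or larger". A one-sided test at 2.5% would give 99.4% for the walk, so the plan's tests are two-sided.

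**Step 2: simple bound.** Three independent main-effect tests at 5%: 1 − 0.95³ = 14.3%.

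**Step 3: the plan's own rule under no effect.** Simulation with 30 per group, two visits and at least 40,000 trials per setting. For each endpoint the interaction is tested at 5%. If it is significant, week 6 and week 12 are each tested at 2.5%; otherwise the group effect averaged over visits is tested at 5%. The table shows the chance that at least one of three endpoints gives a significant group difference, in either direction:

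| Endpoint correlation | Visit correlation 0.25 | 0.50 | 0.75 |
|---|---|---|---|
| 0 | 17.9% | 16.5% | 15.4% |
| 0.5 | 15.7% | 14.9% | 13.5% |
| 0.8 | 12.4% | 11.6% | 10.9% |

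Counting only differences that favour EAA gives 9.2% (endpoint 0, visit 0.25), 8.4% (0, 0.50), 7.3% (0.5, 0.50) and 5.3% (0.8, 0.75).

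**Step 4: where the inflation comes from.** One endpoint alone under the same rule has a rate of about 5-6.5%. The two-stage rule therefore adds little; most of the excess comes from having three endpoints.

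**Step 5: power under a controlled rule, Table 4 inputs.**

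| Endpoint | 5% | 2.5% | 1.67% (5%/3) |
|---|---|---|---|
| 6-minute walk | 99.4% | 98.7% | 98.0% |
| Leg strength | 88.3% | 81.4% | 76.7% |
| Grip strength | 92.4% | 87.2% | 83.5% |

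**The case against.** Several counter-arguments have weight.

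- **A Bonferroni level is already there.** It is, and it keeps each endpoint close to 5%. It does not reach across endpoints.
- **The plan nowhere says that one success is enough.** True. If all three endpoints had to succeed, the false-positive rate would be below 2%. The 11-18% belongs to the any-one reading, which the plan leaves open but does not state.
- **Hypothesis 1 is directional.** A reader might infer an 11-18% chance of falsely claiming improvement. The documents do not support that: those figures count differences in both directions. The rate favouring EAA is about 5-9%, to be set against 2.5%.
- **Week 12 is already implied.** Hypothesis 1 and the Table 4 footnote do point to the final visit, so it would be too strong to say that the time point is wholly open. Still, Section 7.2 tests midpoint and final on equal terms and no section ranks them.
- **Each leg and hand might be tested separately, raising the rate further.** Table 4 has one row and one SD for leg and one for grip, which suggests one value per subject. The fair complaint is that this summary is not defined.
- **The interaction rule must go.** The figures do not require this. It costs little in error rate, and how far an averaged effect would understate the 12-week effect depends on a week-6 effect that the documents do not give.

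**Conclusion.** The concern holds in this form: no endpoint is primary, no rule controls error across the three scheduled function endpoints, and the 12-week change is implied but not designated. If any one success counts, at least one false group difference arises in about 11-18% of trials under no effect, roughly 2 to 3.5 times 5%. About 5-9% favour EAA, a similar multiple of 2.5%.

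The result rests on t-tests standing in for ANCOVA (as Section 7.4 does), the Table 5 visit correlations and the assumed endpoint correlation of 0-0.8. The upper end needs uncorrelated endpoints; at an assumed 0.5 the range is about 13-16%. Even at 0.8 the rate is about double the nominal level. This should be corrected before the data are analysed by group, since a primary test chosen afterwards would not be credible.

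**What to change.** **When.** Before any by-group (A versus B) analysis. Breaking the blind is not a safe deadline: Section 3.5 places it after data entry, but Section 3.6 keeps the product key closed until data analysis ends. Under Section 3.6, coded group results could be seen first. The two sections should be reconciled.

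**What.**
- Name one primary test. Proposal: the week-12 EAA-minus-control contrast for 6-minute walk from the repeated-measures model, two-sided 5%, not conditional on the interaction test.
- If it succeeds, test leg and grip strength at week 12 as key secondaries, using Holm at 5%. Alternatively, use Holm across all three function endpoints with none ranked first.
- Define one summary per subject for the two legs and one for the two hands.
- State whether SF-36 (Hypothesis 2) belongs to this family or is a separately labelled hypothesis with its own level, and name one score. This is the sponsor's choice.
- Insulin sensitivity and plasma lipids may stay secondary, outside the controlled family. The interaction rule may stay as a supportive analysis.
- Restate power at the levels used.

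**Cost.** Wording in Sections 7.1-7.4 and Table 4; no added visits, tests or subjects. The walk has 99.4% power at 5%. With only leg and grip in the gated Holm step, the first level is 5%/2 = 2.5%, so power per test stays at 81.4% and 87.2%. The gate can remove at most 100 − 99.4 = 0.6 points. With three tests in the Holm family (all three function endpoints, or leg, grip and SF-36), the first level is 1.67%: leg 76.7% and grip 83.5%, against 81% and 87% in Table 4. Later Holm steps recover part of that. If gated, the strength endpoints are tested only when the walk succeeds.

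Gait speed being powered but not scheduled, 8/16 weeks in Section 7.5 against weeks 6 and 12 in Section 1.0, and the two statements on lean body mass in Section 7.1 are separate points to reconcile.

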2.0 Hypotheses

1. We propose that 12 weeks of regular consumption of EAA mixture will improve physical function in individuals with heart failure as compared to placebo.
2. We propose that regular consumption of EAA mixture will improve health-related quality of life as compared to placebo.

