3.0 Study Design and Procedures

This is a randomized, double blind, prospective study examining the effects of 12 weeks' ingestion of either EAA mixture or placebo on physical function. We will also examine several blood parameters and fecal microbiome in both groups of subjects (see section 5.1). Up to 80 subjects ages 60 to 89 will be enrolled to obtain 60 completers (30 per group).

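### The treatment-by-time interaction test decides which treatment effect is tested, so the 12-week question in Hypothesis 1 may be answered with a week 6/12 average

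*Combined protocol and SAP*

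**What the plan says.** Section 7.1 fits a repeated-measures ANCOVA with treatment, time and their interaction, and baseline as a covariate. It then reads the interaction test as follows: "A non-significant interaction would imply that the EAA mixture or placebo and time effects are not dependent upon one another", and concludes that main effects can be tested. Interaction and main effects are each judged at 5%.

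Section 7.2 covers the other outcome. After a significant interaction, "This implies the EAA mixture or placebo effect will have to be assessed separately within each time point, and vice versa". The midpoint and final comparisons are then made by separate ANCOVAs at a Bonferroni-corrected level "of 2.5% will be used to determine the statistical significance of these tests".

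Hypothesis 1 in Section 2.0 is that "12 weeks of regular consumption of EAA mixture will improve physical function in individuals with heart failure", compared with placebo. Section 7.3 bases the power calculations only on the case where the interaction is significant. Section 7.4 gives the result for 30 per group at 2.5%: "a two-sample t-test will have approximately 80% power to detect effect sizes of 0.82 standard deviation units or larger". No power is given for the interaction test or for the averaged main effect.

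**The concern.** A non-significant test is not evidence that the treatment effect is constant over time, least of all for an interaction the trial was not sized to detect. Yet here that result settles both what is estimated and the significance level. Baseline is a covariate, so time has two levels and the treatment main effect is the average of the week-6 and week-12 differences.

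If the effect builds after week 6, that average is smaller than the 12-week effect Hypothesis 1 asks about. If an effect is present at week 6 and gone by week 12, the average can still be significant and be read as a benefit of the 12-week regimen. Which quantity the trial reports as its treatment effect is unknown until the data are in.

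**Working it through.** **Inputs from the documents.** 30 completers per group (Sections 3.0 and 7.3); 5% for interaction and main effect (7.1); 2.5% per time point (7.2); Table 4 effect sizes; the correlation grid 0.25/0.50/0.75 from Table 5. Post-baseline tests are at weeks 6 and 12 (Section 1.0). Section 7.5 labels the same two assessments weeks 8 and 16; the sections must be reconciled, but nothing below depends on it.

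**Assumptions.** Normal data, equal SD (set to 1) at both weeks, one endpoint, baseline adjustment already made. Table 5 gives its correlation for the measures; it is applied here to the changes. The effect at week 6 is not in the documents and is varied.

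**Reproducing Table 4.** Two-sided two-sample t-test, 58 df, noncentrality d × √(30/2), level 2.5%. The right-hand column shows the same test at 5%.

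| Endpoint | d | Stated | Recomputed, 2.5% | At 5% |
|---|---|---|---|---|
| 6-minute walk | 105.1/89.3 = 1.177 | 98.67% | 98.67% | 99.4% |
| Leg strength | 11.0/13.3 = 0.827 | 81.31% | 81.38% | 88.3% |
| Grip strength | 4.1/4.6 = 0.891 | 87.19% | 87.19% | 92.4% |
| Gait speed | 0.23/0.28 = 0.821 | 80.80% | 80.80% | 87.9% |

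The plan does not state sidedness; the two-sided test matches its figures.

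**Power of the interaction test.** With standardised effects δ6 and δ12 and correlation ρ, the interaction effect size is (δ12 − δ6)/√(2(1 − ρ)). Take δ12 = 0.82 and δ6 = 0.41:

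| ρ | Interaction effect size | Power at 5% | Missed |
|---|---|---|---|
| 0.25 | 0.41/1.225 = 0.335 | about 25% | about 75% |
| 0.50 | 0.41/1.000 = 0.410 | about 35% | about 65% |
| 0.75 | 0.41/0.707 = 0.580 | about 60% | about 40% |

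**What is tested when it is missed.** (0.41 + 0.82)/2 = 0.615 SD, and 0.615/0.82 = 0.75, so 25% below the week-12 effect. With equal SDs the average and the difference are uncorrelated, so selecting trials with a non-significant interaction does not move that centre.

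**Simulating the whole rule** (at least 60,000 trials per setting; separate runs agree to within about 0.2 points under the null and within 1 point otherwise). Results are for ρ = 0.25/0.50/0.75.

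- Half the effect at week 6: a treatment claim in about 87/83/80% of trials, against 88% for a direct week-12 test at 5%.
- 0.41 SD at week 6 and nothing at week 12: a main-effect or week-12 claim in about 14/11/7%, where a direct week-12 test at 5% would give 5%.
- Full 0.82 SD at both weeks: a main-effect or week-12 claim in about 96/94/91%, against 88% for the direct test.
- No effect at either week: any treatment claim in 6.3/5.7/5.3%; counting only main-effect or week-12 claims, 5.5/5.2/5.0%.

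**Where the null excess comes from.** The averaged branch contributes about 0.95 × 5% = 4.75%. The separate-time-point branch adds about 1.5/1.1/0.7 points, giving roughly 6.3/5.8/5.4%, which matches within simulation error. Under the null the interaction rejects at its own 5% whatever its power elsewhere, so low interaction power is not the cause.

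**The case against.** The strongest defence is that the harm depends on an onset pattern the documents do not give. That is correct. With no effect at week 6 the interaction is detected in 72/88/99% of trials and the plan moves to separate time points as intended. With half the effect at week 6 and correlation 0.75 it is detected in 60%. With the full effect by week 6 nothing is diluted and averaging gains power. A reader might infer that the plan will usually report a diluted effect, or that its estimate is biased toward zero in general; neither can be said without assuming an effect that grows after week 6.

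A reader might also infer that the rule seriously breaks the 5% error rate. It does not: the excess is 0.3 to 1.3 points counting any claim, and at most about half a point counting only claims about the main effect or week 12.

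Nor should the whole power gap against a direct week-12 test be charged to the pre-test. A plain 2.5% test at 0.82 SD has 80.7% power, so much of the gap is the Bonferroni level, which Sections 7.3 and 7.4 disclose and size the trial on. The week-6-only problem also varies: with 0.82 SD at week 6 and none at week 12, a misleading claim occurs in about 15/7/3%, below 5% at the highest correlation.

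Finally, week 12 is not named as the sole time point. Section 1.0 lists comparisons at weeks 6 and 12, and Hypothesis 2 names no time. But Hypothesis 1 does specify 12 weeks, and Table 4 is built on baseline to post-treatment changes. Section 7.1 also never says the interaction term is dropped from the model, so the defect lies in which contrast is tested, not in the model.

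**Conclusion.** The point stands as an error in the decision rule. Section 7.1 draws a conclusion that a non-significant test cannot support, and uses it to choose between a week 6/12 average at 5% and separate time points at 2.5%. For Hypothesis 1 the consequence is a possible change of estimand. If half of a 0.82 SD effect is present at week 6, the interaction is missed in about 40% to 75% of trials and the tested effect is then about 0.615 SD. If 0.41 SD is present at week 6 only, a main-effect or week-12 claim arises in about 7% to 14%. These figures rest on the assumed onset patterns, equal SDs, and Table 5's correlations applied to changes. The type I excess is real but minor and would not by itself justify a change. Multiplicity across endpoints is a separate matter, not counted here. The plan should be corrected before unblinding; the trial's design is not in question.

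**What to change.** Keep the repeated-measures ANCOVA, with treatment, time and their interaction in the model whatever the interaction p-value. Pre-specify the week-12 between-arm contrast from that model, with its confidence interval, as the test of Hypothesis 1 at 5%. Report the week-6 contrast and the interaction as supportive. Delete the sentences in Sections 7.1 and 7.2 that let the interaction result select the test, restate Sections 7.3 and 7.4 to match, and name the time point for Hypothesis 2.

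Power at the Table 4 effect sizes becomes about 99.4% (6-minute walk), 88.3% (leg strength), 92.4% (grip strength) and 87.9% (gait speed), each above the stated figure. If both weeks are to carry a claim, testing both at 2.5% in every case also works: the familywise rate is at most 5% (1 − 0.975² = 4.94% if independent), with the roughly 80% power already stated.

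The cost is wording only, with no extra participants, visits or measurements. The downside is that if most or all of the effect is present by week 6, the averaged test could have had more power: about 91% to 96% against 88% when the effect is full at week 6.
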